4.2 Informed Consent

Prior to undergoing any study-specific tests or procedures, the subject must sign and date the site's current and approved Institutional Review Board (IRB) informed consent form in order to be eligible for study participation. The informed consent will contain all elements required by 21 CFR Part 50 and ISO 14155:2011 and comply with the ethical principles of the Declaration of Helsinki.

4.2.1 Process for Obtaining Informed Consent

The process for obtaining informed consent is outlined below:

- The Investigator or his/her authorized designee conducts the informed consent process
- All aspects of the clinical study that are relevant to the subject's decision to participate will be included in the consent form
- Investigators will avoid any coercion or undue improper influence on, or inducement of, the subject to participate
- The consent process shall not waive or appear to waive the subject's legal rights
- The consent must use native non-technical language that is understandable to the subject
- The Investigator, or designee will provide ample time for the subject to read and understand the informed consent form and to consider participation in the clinical trial
- The consent must include personally dated signatures of the subject and the Investigator, or an authorized designee responsible for conducting the informed consent process, and/or all signatures required by the IRB
- The Investigator, or designee, will provide the subject with a copy of the signed and dated informed consent form

4.3 Study Visits

4.3.1 Screening/Baseline Procedures including NPS Treatment – Visit 1 (Day 0)

The following evaluations and procedures are required at the time of subject screening/baseline

- Signed Informed Consent
- Dermatologic Medical History/Demographics
- Wart classification and anatomic location for all study lesions
- Inclusion and Exclusion criteria

Activities on 1st Study Visit Day - NPS Treatment Day

The following assessments and procedures will be performed

- Using a randomization method, the selected wart(s) will be designated to be treated and one will be designated as an untreated control.
- Each selected lesion will be numerically labeled, and photographic images will be taken before the local anesthetic/numbing.
- Local anesthetic/numbing will be administered to all study lesions.
- NPS treatment #1 will be delivered to all lesions.

- Subject will rate the level of pain from a specified pain score.
- Photographic images of all lesions will be taken immediately post-NPS treatment.
- A light bandage and any PI recommended dressing may be applied.
- Adverse event assessment will be performed.

4.3.2 7-Day Follow-up – Visit 2

The following assessments and procedures will be performed

- Photographic images of all study lesions will be taken.
- Each lesion will be clinically assessed, and the appearance will be rated according to specified criteria.
- Adverse event assessment will be performed.

4.3.3 30-Day Follow-Up / Possible NPS Re-Treatment - Visit 3

The following assessments and procedures will be performed

- Photographic images of all study lesions will be taken.
- Wart reduction assessment, including measurement will be performed.
- All lesions will be clinically assessed, and the appearance will be rated according specific criteria.
- All lesions that are rated other than “Clear” are eligible to receive a retreatment with NPS of those lesions.
- In case of an NPS retreatment:
 - Images of each of the selected lesions will be taken before local anesthetic/numbing and after the NPS treatment.
 - Local anesthesia/numbing will be applied to the identified lesions.
 - NPS treatment will be delivered.
 - Subject will rate the level of pain from a specified pain score.
 - A light bandage and any PI recommended dressing may be applied.
- Adverse event assessment will be performed.

4.3.4 60-Day Follow-Up / Possible NPS Re-Treatment - Visit 4

The following assessments and procedures will be performed

- Photographic images of all study lesions will be taken.
- Wart reduction assessment, including measurement will be performed.
- All lesions will be clinically assessed, and the appearance will be rated according specific criteria.
- All lesions that are rated other than “Clear” are eligible to receive an NPS retreatment of those lesions.
- In case of an NPS retreatment:

- Images of each of the selected lesions will be taken before local anesthesia/numbing and after the NPS treatment.
- Local anesthesia/numbing will be applied to the identified lesions.
- NPS treatment will be delivered.
- Subject will rate the level of pain from a specified pain score.
- A light bandage and any PI recommended dressing may be applied.

- Adverse event assessment will be performed.

4.3.5 90-Day Follow-Up / Possible NPS Re-Treatment- Visit 5

The following assessments and procedures will be performed

- Photographic images of all study lesions will be taken.
- Wart reduction assessment, including measurement will be performed.
- All lesions will be clinically assessed, and the appearance will be rated according specific criteria.
- All lesions that are rated other than “Clear” are eligible to receive an NPS retreatment of those lesions.

- In case of an NPS retreatment:
 - Images of each of the selected lesions will be taken before local anesthetic/numbing and after the NPS treatment.
 - Local anesthesia/numbing will be applied to the identified lesions.
 - NPS treatment will be delivered.
 - Subject will rate the level of pain from a specified pain score.
 - A light bandage and any PI recommended dressing may be applied.

- Adverse event assessment will be performed.

4.3.6 120-Day Follow-Up – Visit 6 (Final Study Visit)

The following assessments and procedures will be performed

- Photographic images of all study lesions will be taken.
- Wart reduction assessment, including measurement will be performed.
- All lesions will be clinically assessed, and the appearance will be rated according specific criteria.
- Adverse event assessment will be performed.
- Subject satisfaction will be evaluated for the appearance of the treated lesions.

Table 2 lists assessments and procedures required at each study visit.

Table 2 : Schedule of Events and Evaluations

Study Visit Interval	#1 0-days Enrollment NPS TX #1	#2 7-days Post-NPS TX #1	#3 30-days Post-NPS TX #1	#4 60-days Post-NPS TX #1	#5 90-days Post-NPS TX #1	#6 120-days Post-NPS TX#1 (Final Visit)
Study Visit Description	Informed Consent All eligibility criteria met TX #1 Photographic images	Lesion(s) evaluation Photographic images	Lesion(s) evaluation TX #2 (if applicable) Photographic images	Lesion(s) evaluation TX #3 (if applicable) Photographic images	Lesion(s) evaluation TX#4 (if applicable) Photographic images	Lesion(s) evaluation Subject Satisfaction Photographic images
Visit Range (# of Days Post-NPS TX #1)		5-9 days	27-37 days	57-67 days	87-97 days	120-130 days

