Nineteen (19) treated adult subjects were required to have 2-5 non-genital, off-face cutaneous warts in this multi-center feasibility study. Up to four warts were designated to be treated, while one wart was designated as the sham control. Subjects received an initial NPS-treatment and returned for 3 to 5 follow-up evaluations at 7 days, 30 days, 60 days, 90 days and 120 days after the initial treatment. Each wart was evaluated for size reduction and the condition of the skin. If the reduction in wart size met study criteria, the wart was eligible for an additional treatment and at the discretion of the investigator.

Six (6) of the 19 subjects were male and 13 were female. Ages ranged from 23 to 71, with an average age of 48. Subjects had Fitzpatrick skin types ranging from I to III. A total of 58 warts have been included in the study at the time of this report. 34 warts were identified for treatment and 19 warts as controls. 70% of the study warts had been previously treated with another modality and were not successful at eliminating the wart. 69% of treated warts were located on the hand/fingers and the remaining 31% of treated were located on the feet. Twenty-five (25%) of treated warts received a single treatment, and 75% received two treatments. Of the treated warts, 50% showed 100% reduction in size, 21% showed a 50-90% reduction in size, and 26% showed less than a 50% reduction in size at the last reported visit. Twenty-nine (29%) of the treated warts showed 100% reduction after a single treatment. There were two instances where the control wart showed 100% reduction in size, suggesting that there may be an immune response. Preliminary data analysis indicates that complete coverage of the wart within the treatment zone is required. There is also a trend toward the use of higher settings within the allotted range for better outcomes. There were no instances of hypopigmentation noted, and 3 cases of mild hyperpigmentation at 60 days.

The high rate of wart size reduction suggests the utility of the unique NPS cellular mechanism for the treatment of non-genital, cutaneous warts. Based on these initial results, a larger pivotal study is warranted and will be conducted in the future to further evaluate the use of NPS technology for the treatment of warts.

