3.2 Study Design Overview

The study is designed as a prospective, non-randomized, multicenter pivotal study to evaluate the safety and effectiveness of the CellFX System in patients with non-genital warts, excluding the face. Macrophotography of all treated warts will be captured along with Investigator assessments using a wart measurement scale and tissue response. One of the warts for each subject will be untreated and will serve as the subject's internal control. Please note the Investigator has the option at baseline and at each follow-up visit for curettage of the targeted site prior to NPS treatment. Additionally, at the 30-day, 60-day and 90-day visits the Investigator has the option to retreat any previously treated lesion.

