4.0 STUDY PROCEDURES

4.1 Subject Selection

4.1.1 Inclusion Criteria:

Subjects are required to meet **ALL** inclusion criteria in order to be enrolled in the study.

1. Subjects must be at least 21 and not older than 80 years of age.
2. Subjects must be able to read and speak English or Spanish.
3. Subjects must sign a written informed consent to participate in the study, prior to any study related procedures.
4. Subject must have a minimum of two cutaneous non-genital warts, each not exceeding 10 x 10mm.
5. Subject is willing to undergo all study-mandated procedures.
6. Subject agrees to refrain from using all other wart removal products or treatments (topical medication including over-the-counter medications) during the study period.

4.1.2 Exclusion Criteria:

Subjects who meet **ANY** of the following exclusion criteria will not be enrolled in this study.

1. Subject has an implantable electronic medical device. (pacemaker, implantable cardioverter defibrillator, etc.)
2. Subject has cochlear implants.
3. Subject has an active systemic infection or history of an infection in the designated treatment area within 90 days of enrollment.
4. Subject has a history of and/or current tinnitus.
5. Subject is known to be immune-compromised.
6. Subject is taking a blood thinning medication (Antiplatelet, Anticoagulation, Factor Xa Inhibitor, etc.)
7. Subject has Type 1 Diabetes and is insulin dependent.
8. Subject has a known allergy to Lidocaine or Lidocaine-like products.
9. Subject is a member of a vulnerable population including individuals employed by the Sponsor, clinic site, or entity associated with the conduct of the study.
10. Subject has a comorbidity or condition which may reduce compliance with this protocol, including follow-up visits.
11. Subject is participating in another research study involving an investigational agent (pharmaceutical, biologic, or medical device).

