7.5 Protocol Deviations

A protocol deviation is defined as an event where the Investigator or site personnel did not conduct the study according to the study protocol or the Investigator Agreement.

Major deviations include those that involve the primary endpoint, the informed consent process and the inclusion/exclusion criteria of the study, or any deviation that involves or leads to a serious adverse event in a study subject.

Deviations shall be reported to the study Sponsor regardless of whether medically justifiable, pre-approved, or taken to protect the patient in an emergency. Patient specific deviations will be reported on the Case Report Form. Investigators will also adhere to procedures for reporting study deviations to their IRB in accordance with their specific IRB reporting policies and procedures. Deviations from the study protocol will be reviewed and evaluated by the Sponsor on an ongoing basis and, as necessary, appropriate corrective actions put into place.

GCP regulations require that Investigators maintain accurate, complete and current records, including documents showing the dates and reasons for each deviation from the protocol.

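### The Visit 1 procedure list sets one wart aside as an untreated control, then directs NPS treatment #1 to every lesion without excepting it

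*Protocol*

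**What the plan says.** Section 3.2 of the protocol (Study Design Overview) sets a within-subject comparison: "One of the warts for each subject will be untreated", and that wart is the subject's internal control. The same section limits later treatment, since at the 30-, 60- and 90-day visits "the Investigator has the option to retreat any previously treated lesion".

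Section 4.3.1 turns this into a list of treatment-day steps. The first bullet uses a randomization method to decide which warts are treated and adds that "one will be designated as an untreated control". The third bullet gives local anesthetic to all study lesions. The fourth reads "NPS treatment #1 will be delivered to all lesions". It makes no exception, and no later text supplies one.

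Inclusion criterion 4 in section 4.1.1 sets the smallest possible comparison: "Subject must have a minimum of two cutaneous non-genital warts". Section 3.3 plans about 60 subjects at 6 sites.

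**The concern.** The fourth bullet, taken as written, sends the control wart for treatment. A site cannot then satisfy the whole list. Treating the control departs from section 3.2 and the first bullet, and sparing it departs from the fourth. Section 7.5 defines a deviation as an event where site staff "did not conduct the study according to the study protocol", and on a literal reading either course meets that definition.

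The study is non-randomized between subjects, so the untreated wart is its only concurrent comparator. That comparator matters in this condition. Section 1.1 describes warts as usually self-limited, and the feasibility study summarized under section 1.4 reports that "There were two instances where the control wart showed 100% reduction in size". Without an untreated wart in the same person, clearance of treated warts cannot be separated from spontaneous clearance. A control treated at Visit 1 cannot be recovered later.

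**Working it through.** The protocol gives no sample-size, power or error-rate figure that bears on this point. The check is a comparison of text followed by a count.

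**Step 1. Which warts receive NPS at Visit 1?**

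| Place | Instruction | Control wart |
|---|---|---|
| 3.2 | One wart per subject is left untreated | Spared |
| 4.3.1, bullet 1 | One wart is designated as the control | Spared |
| 4.3.1, bullet 4 | Treatment #1 goes to every lesion | Treated, if read literally |

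**Step 2. Could 'lesions' mean treated warts only?** The protocol has no such definition. Baseline classification in 4.3.1 covers all study lesions, which naturally includes the control. Where the authors want the narrower group they say so. Section 3.6.1 scores each treated wart, section 3.2 restricts retreatment to lesions already treated, and section 4.3.6 says "Subject satisfaction will be evaluated for the appearance of the treated lesions". Bullet 4 has no such limit.

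A silent narrow reading also causes trouble elsewhere. In 4.3.3 to 4.3.5 the same unqualified phrase governs both the clinical assessment and the retreatment bullets. If it means treated warts only, the assessment bullet no longer requires the control to be rated. If it includes the control, bullet 4 of 4.3.1 treats it.

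**Step 3. Does the retreatment limit in 3.2 repair the problem?** No. A control treated at Visit 1 has become a previously treated lesion, so the limit no longer protects it. Section 3.4 and the retreatment bullets in 4.3.3 to 4.3.5 do not except the control either.

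**Step 4. Count.** The inputs are a minimum of 2 warts per subject (4.1.1), 1 control per subject (3.2) and about 60 subjects (3.3).

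- Two-wart subject, bullet 1: 2 − 1 = 1 treated, 1 control.
- Two-wart subject, bullet 4 read literally: 2 treated, 0 controls.
- Whole study, design as stated: about 60 × 1 = about 60 controls.
- Whole study, bullet 4 followed literally for every subject: 60 × 0 = 0 controls.

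**Step 5. Background on why a control is needed.** The feasibility summary gives 19 control warts, of which 2 cleared completely: 2/19 = 0.105, or 10.5%. The exact (Clopper-Pearson) 95% interval is 0.0130 to 0.3314, or 1.3% to 33.1%. This describes another, earlier study. It is not a forecast for this one and does not measure the effect of the wording.

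**The case against.** The strongest reply is that the intent is settled within the same list. A procedure list is read in order, and a wart just designated as untreated falls outside a later treatment step. Section 3.2 says the same. Lesions are numerically labeled on the day, sites are trained on the protocol (7.2), and monitors verify procedural data against source documents (7.8). Nothing suggests that any control would in fact be treated, or that sparing one would be logged as a deviation. The contrast of 60 against 0 needs every site to misread the list for every subject. The primary assessment concerns treated warts and survives in any case.

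The feasibility figure is open to question too. That study used a sham control, whereas this one leaves the wart untreated. Its counts also do not fully reconcile, since 34 treated plus 19 control warts make 53, against 58 reported as included.

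Much of this stands. The intended reading is recoverable, the count is an outer bound, and the feasibility rate is only background. Retreatment also presupposes an earlier treatment, which weakens the case against the later-visit wording taken alone. What does not follow is that bullet 4 may stay as it is. Recoverable intent makes an error less likely but does not make the instruction correct. A step that decides which warts receive the device should not depend on another bullet or section to be carried out safely. Training and monitoring are safeguards against misreading, and monitoring against source may find an error only after the control has been treated.

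**Conclusion.** The concern holds. Section 4.3.1 contradicts itself and section 3.2 on whether the control wart is treated at Visit 1, and no definition or later text resolves it. This is a drafting error in an operative list. The design itself is clearly stated and is not in question.

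The largest possible consequence is loss of the untreated wart in every subject: about 60 controls reduced to none, or 1 to 0 for each subject. This rests on literal compliance throughout. No misreading rate is assumed, and the likely number of controls treated in error is small. The primary assessment could still be computed, but for each affected subject the reference needed to interpret it would be lost for good. It should be fixed, because the harm, though unlikely, is irreversible and the correction costs almost nothing.

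**What to change.** Reword the fourth treatment-day bullet of 4.3.1 along these lines: *NPS treatment #1 will be given to all lesions designated for treatment; the control wart receives no NPS through Visit 6.*

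Two further clarifications are optional:

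- In 3.4, 4.3.3, 4.3.4 and 4.3.5, limit the retreatment wording to lesions already treated, as 3.2 does. Leave the assessment bullets covering every study lesion, so that the control is still rated.
- State in the anesthetic bullet of 4.3.1 whether the control wart is numbed.

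The essential change is one phrase in one bullet. The retreatment edit touches four more places and the anesthetic point one more bullet. No patients, visits or procedures are added.

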1.2 Non-Surgical Approach

Chemical Destruction:

Salicylic Acid

The use of salicylic acid is one of the two most commonly used treatments for warts. Dermatologists prescribe chemical destruction treatments where patients apply an over-the-counter preparation, usually less than 17% salicylic acid or prescription salicylic acid containing up to 70% salicylic acid at home every day. Treatment response rates of 40-84% with an average of 61% have been reported as an effective therapy for non-genital cutaneous warts.¹ Minor skin irritation was reported occasionally in some of the other trials, but generally there were no major harmful effects of topical salicylic acid.² A systematic review of local treatments of cutaneous warts by Mitsuishi et al., found evidence that topical treatments with salicylic acid have a therapeutic effect, with a cure rate of 75 percent compared with 34-48 percent in placebo controls.^{1,3} Other agents used for chemical destruction are monochloracetic acid, dichloracetic acid, trichloroacetic acid, silver nitrate, glycolic acid and 80% phenol in solution. Complications associated with using chemicals include pain, hyperpigmentation, hypopigmentation, burning sensation and erythema.⁴

Cantharidin

Cantharidin is used as an agent in the clinic by "painting" the wart causing oxidative stress by inhibiting phosphatases 1 and 2A that damages both DNA single- and double-strand breaks and triggers p53 dependent apoptosis.⁴ Cantharidin causes a blister to form under the wart. In a week or so, the patient returns to the office and the dermatologist clips away the dead wart.

Immune Modulators

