3.0 PROTOCOL

3.1 Study Purpose and Objectives

The purpose of this study is to evaluate the safety and effectiveness of the CellFX System in patients with cutaneous non-genital warts on all areas of the body, excluding the face.

The study objectives are listed below:

- Evaluate the condition of skin in the treatment areas (erythema, etc.) over the course of 7 to 120 days post-initial NPS treatment
- Evaluate the overall response to NPS treatment by:
 1. Wart clearance (generally accepted as complete clearance of warts from the treated area)
 2. Wart reduction (reduction in the total number of warts)
- Evaluate and assess adverse effects of treatment

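### Skin condition is the first-listed objective, yet no appearance rating is listed before treatment at Visit 1, so per-lesion attribution to NPS rests on photographs that no step rates

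*Protocol*

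**What the plan says.** The first objective in Protocol 3.1 is to "Evaluate the condition of skin in the treatment areas (erythema, etc.) over the course of 7 to 120 days post-initial NPS treatment".

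The ratings that serve it begin at the Day 7 visit (4.3.2): "Each lesion will be clinically assessed, and the appearance will be rated according to specified criteria". Sections 4.3.3 to 4.3.6 repeat a rating of this kind for all lesions at Days 30, 60, 90 and 120.

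Before treatment, Visit 1 (4.3.1) characterises the lesions through "Dermatologic Medical History/Demographics", "Wart classification and anatomic location for all study lesions", and photographs of each numbered lesion taken ahead of the anesthetic. It lists no rating of skin condition or appearance. In Table 2 the Visit 1 description reads "Informed Consent All eligibility criteria met TX #1 Photographic images"; a lesion evaluation entry stands in the other five columns only.

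On the likely state of the skin at entry, 1.4 reports for the sponsor's feasibility study (NP-WF-007) that "70% of the study warts had been previously treated with another modality and were not successful at eliminating the wart". Section 1.2 says of one class of earlier treatment: "Complications associated with using chemicals include pain, hyperpigmentation, hypopigmentation, burning sensation and erythema". Section 9.1 names pigment change and scarring among the risks of the study device.

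**The concern.** A rating that starts only after treatment has no baseline on its own scale. A mark left by an earlier treatment can be scored at Day 7 and later as though NPS had caused it, which overstates harm. The investigator may equally discount a new mark as old, which understates it. The documents do not show which of these would dominate.

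The rating matters more here because little else captures these findings in a structured way. The reportable events in Table 3 are infection, bleeding and pain; pigment change, scarring and erythema are not among them. Section 5.0 records adverse events that are device or procedure related and leaves that judgement to the investigator. The judgement depends on knowing how the lesion looked beforehand.

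**Working it through.** No formula applies and the plan states no figure to reproduce. The check sets the visit lists side by side and then asks what else could serve as a baseline.

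**1. Count of ratings per lesion**

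| Visit | Day | Appearance rating listed in 4.3 | Lesion evaluation in Table 2 |
|---|---|---|---|
| 1 (pre-treatment) | 0 | No | No |
| 2 | 7 | Yes | Yes |
| 3 | 30 | Yes | Yes |
| 4 | 60 | Yes | Yes |
| 5 | 90 | Yes | Yes |
| 6 | 120 | Yes | Yes |

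Pre-treatment ratings: 0. Post-treatment ratings: 5. Pre-treatment photograph sets: 1 per lesion.

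**2. Can pre-existing change enter the study?** Nothing in 4.1.2 excludes previously treated warts. Inclusion criterion 6 in 4.1.1 bars other wart treatments during the study period and sets no interval before it. In the feasibility study 70% of warts had been treated before. The effects that 1.2 ascribes to chemical treatment (pigment change, erythema) overlap with the device risk of pigment change in 9.1; 1.2 also mentions dark spots after cryotherapy in dark skin. Entry with pre-existing change is therefore plausible.

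**3. How often?** If the feasibility proportion carried over and a fraction r of previously treated warts kept a visible mark, the affected share from this source would be 0.70 × r. The documents give no value for r. Over its whole range, 0 to 1, the share runs from 0% to 70%, which settles nothing. No magnitude is claimed.

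**4. What could stand in for a baseline rating?**
- Photographs (4.3.1): one pre-treatment set per lesion, but no step rates them or names them as the baseline. Section 3.2 allows curettage at baseline before NPS, and its order relative to the photograph is not stated.
- History (4.3.1): collected, but prior treatment of each lesion is not specified.
- Control wart (3.2, 4.3.1): a concurrent comparison at group level. It cannot show whether a mark on one particular treated wart is new, because warts in one subject may have different treatment histories.
- The control's status: 3.2 leaves one wart per subject untreated, while 4.3.1 delivers the first NPS treatment to every lesion. These passages must be reconciled before the comparison can be relied on.

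**The case against.** The strongest reply is that a baseline exists in substance. Every lesion is numbered and photographed before anesthetic, and pigment change, scarring and erythema are visible findings that a later reader could score. Section 4.3.1 designates treated and control warts by a randomization method, so residue from earlier treatment should balance in expectation, and follow-up ratings cover all lesions. Section 8.4 also requires records of each subject's condition on entry.

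Much of this stands. A reader might infer that old and new skin changes cannot be separated at all; the photographs and the control wart rule that reading out. What remains is narrower. Scoring photographs later is a different method from clinical assessment, and no step calls for it. The control comparison works for groups, not single lesions. The records in 8.4 are kept per subject and are general.

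A reader might also infer that pre-existing change is as common as the hyperpigmentation signal in the feasibility study: 3 cases with 34 warts identified for treatment, 3/34 = 8.8% if each case is one treated wart. Assuming that 5% to 15% of previously treated warts carry residue gives 0.70 × 0.05 = 3.5% to 0.70 × 0.15 = 10.5%, which looks similar. The 5% to 15% has no source in the documents, and the similarity follows wholly from that choice. Section 1.4 does not say which earlier treatments were used, and 1.2 describes cryotherapy as leaving little or no scarring. The comparison is not supported.

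Two further points are fair. Table 2 is abbreviated: its Visit 1 column also omits history, pain score and adverse event assessment, so the weight rests on 4.3.1. The rating criteria and case report form are not shown. Some items may describe response to treatment and have no pre-treatment score, and the form may already hold a baseline field. Reporting conventions may sit in an analysis plan, but that plan cannot supply a clinical rating that was never made.

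**Conclusion.** The point holds in a limited form. As written, the protocol lists 0 pre-treatment and 5 post-treatment ratings of lesion appearance, so its first-listed objective has no baseline on its own scale. Attribution of a skin finding on a given lesion relies on photographs that the protocol does not say will be rated. Attribution across the group relies on a control wart whose untreated status the text contradicts. The size of any resulting bias is unknown, and its direction could be either.

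This rests on two assumptions: that the Visit 2 to 6 criteria include skin items such as erythema, pigment change or scarring, as the objective suggests; and that no baseline field exists on the unseen form. If such a field exists, the protocol should say so. The change is worth making because it is cheap and because a pre-treatment clinical rating cannot be obtained once the lesion has been treated.

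**What to change.** 1. In 4.3.1, before anesthetic, any curettage and NPS, add a rating of every study lesion, treated and control, on those skin-condition items of the Visit 2 to 6 criteria that can be scored before treatment (for example erythema, pigment change, scarring).
2. Add the lesion evaluation entry to the Visit 1 column of Table 2.
3. Report skin findings as new or worsened relative to that rating.
4. Reconcile the wording in 4.3.1 that gives the first NPS treatment to every lesion with the untreated control described in 3.2.

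The cost is a slightly longer Visit 1: a few minutes for each of about 60 subjects, at a visit where every lesion is already classified, numbered and photographed.
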